9. SAFETY MONITORING AND STOPPING GUIDELINES

Interim monitoring plans and stopping guidelines will be defined by the DSMB. This section describes proposed plans. The study is expected to take three years to complete. Stopping guidelines are proposed for two outcomes, serious infection and pain crisis requiring ED or hospital admission. For these two outcomes, yearly looks at the data will take place. Therefore, three looks at the data (including the final look) are anticipated.

In designing the study, a serious infection difference of 20% between the 2 arms would be of clinical interest. As we do not expect to have adequate power in this study of 30 subjects to detect this difference, with an alpha of 0.05 with 15 in each arm, we will be able to detect an infection rate difference of 47-56% between the two arms. Any statistically significant difference in serious infection or pain admissions between the two arms will be considered as evidence for stopping the clinical trial.

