10. STATISTICAL CONSIDERATIONS

10.1. Sample Size and Power

Participants will be recruited from UNC and Emory for this proposal. There are about 50 eligible patients at UNC and about 100 chronically transfused subjects at Emory. We anticipate no difficulties reaching our 40 patient study target. We anticipate that we will enroll at least 40 total individuals aged 16-60 years who are managed with chronic transfusions at UNC or Emory and will meet the study inclusion and exclusion criteria. This study will not attempt to stratify the study population for age or gender.

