10.2. Analysis Plan

The analysis will be an intent to treat (ITT) with all those randomized being included in the study. For all aims, the distribution of, and relationship between, variables will be explored with summaries, plots, and tree analysis. All statistical estimates of population parameters will be tabulated along with corresponding confidence intervals (CIs). All hypothesis tests yielding large p-value (e.g., $p > \alpha$) will be reported as being inconclusive. [name], the lead biostatistician, or her designee, will perform these analyses. Where necessary for parametric assumptions, appropriate transformations will be employed with justification for their use; otherwise, non-parametric tests will be used. P-values will be reported without dichotomization wherever applicable. Data obtained from transfusion events where units of the appropriate age could not be obtained (study deviation) will be excluded from a subanalysis of the dataset, and the same distribution of, and relationship between, variables will be explored with similar summaries, plots, and tree analysis as in the ITT analysis. All subjects, regardless of age and gender, will be analyzed together as one cohort. Statistical software used in this study will be Cytel, StatXact and LogXact, SAS version 9.4, and Salford systems CART (Classification and Regression Trees). To adjust for multiple comparisons, we will use the false discovery rate approach which is less conservative than the Bonferroni approach. *Missing data:* Logistic regression will be used to investigate the possible causes for missing data and to investigate if data are missing at random (MAR). Reasons for missing data will be documented in the study database. We do not anticipate any missing data or drop-outs, but we will monitor these events. Assuming data are MAR, multiple imputations will be used for items, and for repeated measures, a random effects models will be used; the structure for the variance covariance matrix will be explored under the constraints of sample size. A sensitivity analysis will also be performed to evaluate the robustness/fragility of the study's main results to reasonable perturbations of the statistical methods and assumptions used. Results of the sensitivity analyses will only be used to guide trust in the main results.

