The primary outcome measure is the change in CD62L (activated) circulating monocyte/macrophage MFI at 2 hours post-transfusion compared to the subject pre-transfusion. We will compare the two groups (\geq 30 day-old compared to \leq 10 day-old unit exposure) using a two sample two-sided t-test of the log at an alpha of 0.05. Power: We will have at least 80% power to detect a change in the ratio of 1.35 post-transfusion if the variability is similar to that seen in our preliminary data.

Exploratory: We will use a general(ized) linear model to include biochemically old units transfused (Aim 1 outcome), regardless of unit age, as a covariate in our analysis. Other co-variates in this model will include free heme, cell free hemoglobin, and NTBI. We will similarly compare other obtained activation measures as outcomes: activation markers for monocytes, neutrophils (as listed in section 6) and measured plasma cytokine

concentrations (section 6). We will also plan for auxiliary analyses of the outcome variables in which the explanatory variable is the age (days) of the RBC units --to characterize the degree to which age (days) can accurately predict the clinical and physiologic outcome measures defined. Lastly, as an exploratory aim, we will evaluate the *in vivo* change in recipient red cell PE/PS positivity at 2 and 24 hours post transfusion.

Aim 3:

The primary outcome variable is the rate of post-transfusion infections in the patient. The primary estimand is the treatment effect defined as the difference between the regimen-specific proportions of patients in the target populations that would experience post-transfusion infections. This population parameter will be estimated as a function of the proportions observed in the sample of patients studied. The point estimate will be reported along with the corresponding 95% confidence interval estimate. The presence of an indwelling catheter will be used as a key co-variate in this analysis. *Power:* A difference of 20% will be of clinical interest. We do not expect to have adequate power for this pilot study but at an alpha of 0.05 with 20 subjects in each group we will be able to detect a difference of 47% between the proportions.

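### The only performance figure behind Section 9's proposed stopping guideline is for 30 subjects and one full-enrolment test, not for the 40-patient target or either interim look

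*Combined protocol and SAP*

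**What the plan says.** All references are to the combined protocol and SAP.

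- **Section 9, status.** "Interim monitoring plans and stopping guidelines will be defined by the DSMB. This section describes proposed plans". Looks are yearly, three including the final one, on serious infection and on pain crisis leading to an ED visit or admission.
- **Section 9, criterion.** "Any statistically significant difference in serious infection or pain admissions between the two arms will be considered as evidence for stopping the clinical trial". No test, per-look alpha or number of patients per look is given.
- **Section 9, performance.** "a serious infection difference of 20% between the 2 arms would be of clinical interest". Then: "As we do not expect to have adequate power in this study of 30 subjects to detect this difference", and "with 15 in each arm, we will be able to detect an infection rate difference of 47-56% between the two arms". Nothing is given for pain admissions.
- **Section 10.1.** "We anticipate no difficulties reaching our 40 patient study target".
- **Section 10.2.1, Aim 3.** Power for 20 points is again called inadequate, but "at an alpha of 0.05 with 20 subjects in each group we will be able to detect a difference of 47% between the proportions".
- **Section 10.2.** "P-values will be reported without dichotomization wherever applicable". Estimates are to carry confidence intervals, and large p-values are to be called inconclusive.
- **Section 8.6.** The DSMB receives arm assignments and the number of subjects per arm with an infection leading to an ED visit or admission, with a p-value. That comparison is said to carry no formal stopping rule. The same list asks the DSMB to evaluate whether serious infection or pain admissions differ significantly.

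**The concern.** The DSMB will build its guideline from Section 9. The one number there on how well the comparison works belongs to a smaller trial than the one being run, and to a single test after everyone is enrolled. The trial can stop early only at the first two looks, and for those the section gives nothing.

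Significance is also the only evidence for stopping that Section 9 names. If the p-value is the main thing read at an interim look, a non-significant result could be taken as reassurance when the data could hardly have shown a difference of the size the section cares about. Sections 8.6 and 9 do not carry over the reporting principles of 10.2. They also leave open whether serious infection is the 8.6 outcome, for which 8.6 says there is no formal rule.

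**Working it through.** **Inputs from the documents.** Alpha 0.05; 15 per arm (Section 9); 20 per arm (Aims 1 and 3); differences of 20 and 47 points; three looks.

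**Assumptions.** Section 9 states none of these: two-sided Fisher test (named for Aim 1 and for the exploratory group comparisons in Aim 3); 80% power (stated for Aim 1); one yes/no result per patient; a range of lower-arm rates; looks near one third and two thirds of enrolment.

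**Formulas.** For n per arm, power = sum over a, b of Bin(a; n, p1) x Bin(b; n, p2) x [1 if Fisher p(a, b) <= 0.05, else 0]. The detectable difference is the smallest d for which power at (p, p + d) reaches 0.80. The chance of a signal by look 2 is 1 minus the probability of p > 0.05 at both looks, by exact enumeration.

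**Step 1: Section 9's own figure.** At 15 per arm, d is 47 points at a lower rate of 4% or 50%, and peaks at 56 points at 20-25%. So 47-56% reproduces as one test at 15 per arm.

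**Step 2: the same calculation at other sizes** (points; lower rates 5%, 10%, 20%)

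| Per arm | 5% | 10% | 20% |
|---|---|---|---|
| 7 | 78 | 78 | 77 |
| 14 | 50 | 54 | 58 |
| 15 | 49 | 54 | 56 |
| 20 | 39 | 43 | 47 |

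At 20 per arm the value is 48 at lower rates of 25-30%. Aim 3's 47% matches a lower rate of 20%. The 40-patient range is therefore about 39-48 points for lower rates of 5-30%.

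**Step 3: a true 20-point difference at the interim looks.** One case can be checked by hand. At 7 per arm with none in one arm, significance needs 5 of 7 in the other. For 0% v 20% that is P(Bin(7, 0.2) >= 5) = 0.0043 + 0.0004 = 0.005 (the term for 7 of 7 is negligible). At 13 per arm it again needs 5 events: P(Bin(13, 0.2) >= 5) = 0.099.

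Chance of a signal by look 2 (%):

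| Looks 1 and 2 | 0 v 20 | 10 v 30 | 20 v 40 | 30 v 50 |
|---|---|---|---|---|
| 7, 13 per arm | 10 | 12 | 12 | 13 |
| 7, 14 per arm | 13 | 14 | 13 | 12 |
| 8 v 7, 14 v 13 (lower rate in larger arm) | 25 | 22 | 20 | 17 |
| 5, 10 per arm (30 patients) | 3 | 7 | 8 | 8 |

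Near-equal arms are included because blocks of 5 cannot split evenly. Silence through look 2 is thus about 75-90% on the 40-patient schedules, and about 92-93% on the 30-patient schedule for lower rates of 10-30%. With a lower rate of zero the latter reaches 97%.

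A single Fisher test needs at least 24 per arm for a 50% chance at 0% v 20%, and 33-58 per arm for lower rates of 5-40%. That exceeds the whole trial, so the direction does not depend on the assumed look sizes.

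**Step 4: a true 47-point difference.** With lower rates of 10-30%, a signal by look 2 occurs in 59-69% of trials at 7 then 13 or 14 per arm.

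**Step 5: what a p-value alone hides.** Infection in 3/14 v 6/14 is a 21-point difference with Fisher p = 0.42. The Newcombe 95% CI runs from -12 to 50 points.

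**The case against.** The strongest reply is that the plan already admits the main limitation. Section 9 and Aim 3 both say power for 20 points is inadequate, and Section 2.1 calls this a feasibility study. If full enrolment is underpowered, so is any interim look. That stands: the calculation gives the size of a conceded limit and uncovers no hidden one. The admission in Section 9 is still made for 30 subjects at full size.

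The stale figure is also mild. It contains Aim 3's 47%, is otherwise more pessimistic, and 30 is the low end of the site projections in the synopsis (15 + 5 + 10 = 30, up to 15 + 10 + 20 = 45). A reader might infer that Section 9 overstates its sensitivity; at full enrolment it does not. But 30 is not the target.

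A reader might also infer that significance stops the trial automatically, or that the DSMB sees nothing else. The text does not support this. Significance is evidence within a guideline the DSMB will define, and 8.6 supplies infection counts by arm, mortality, serious adverse events and unexpected events. For infection the risk difference can be worked out from what is supplied. For pain admissions 8.6 lists no counts, and the serious-event definition in 8.1 leaves out usual pain crises.

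A third tempting reading is that repeated unadjusted looks endanger Aim 2. If 20 per arm gives 80% power, stopping at 7 per arm would leave about 35%. But at 7 per arm a false signal on either outcome at look 1 occurs in 0.04-2.6% of trials (event rates 10-50%, independent outcomes). Even with arms of 8 v 7 it is 0.3-6.9%, and a signal is not a stop. This gives no ground for a tighter threshold.

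Finally, the rates depend on the assumptions. Unadjusted chi-square would raise detection of 20 points by look 2 to 24-27% at 7 and 13 per arm. The direction holds.

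**Conclusion.** The concern holds in a limited form and should be fixed. The conflict between 30 subjects at 15 per arm and the 40-patient target is plain on the page and needs no assumption. The 47-56% figure describes one full-size test at 15 per arm; the 40-patient equivalent is about 39-48 points at 80% power.

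At the interim looks, significance is a weak safety signal. A true 20-point difference in one outcome goes undetected through look 2 in roughly 75-93% of trials, while a 47-point difference is detected in about 60-70%. These two ranges rest on Fisher p <= 0.05, the assumed look sizes and the scanned event rates, so they show the order of magnitude only. They do not show that the DSMB is bound by significance, that the plan hides its low power, or that the threshold should change.

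The wording of 8.6 and Section 9 on infection also needs reconciling.

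**What to change.** 1. In Section 9, replace 30 subjects, 15 per arm and 47-56% with 40 subjects, 20 per arm and a figure consistent with Aim 3 (about 39-48 points at 80% power for lower-arm rates of 5-30%). Say that it applies to one test at full enrolment.
2. In 8.6 and 9, for both infection and pain admissions, report counts by arm and the risk difference with 95% CI beside the p-value. State that a non-significant interim result is inconclusive, in line with 10.2.
3. Say whether serious infection in Section 9 is the 8.6 outcome (infection leading to an ED visit or admission), and reconcile the absence of a formal rule there with the guideline proposed in Section 9.
4. Optional: name the test, and attach a by-look table of false-signal and detection chances with its assumptions stated.

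The cost is wording in two sections. No patients or data are added, since 8.6 already gives the DSMB each subject's arm. No stopping threshold is proposed or altered.

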10. STATISTICAL CONSIDERATIONS

10.1. Sample Size and Power

Participants will be recruited from UNC and Emory for this proposal. There are about 50 eligible patients at UNC and about 100 chronically transfused subjects at Emory. We anticipate no difficulties reaching our 40 patient study target. We anticipate that we will enroll at least 40 total individuals aged 16-60 years who are managed with chronic transfusions at UNC or Emory and will meet the study inclusion and exclusion criteria. This study will not attempt to stratify the study population for age or gender.

10.2. Analysis Plan

The analysis will be an intent to treat (ITT) with all those randomized being included in the study. For all aims, the distribution of, and relationship between, variables will be explored with summaries, plots, and tree analysis. All statistical estimates of population parameters will be tabulated along with corresponding confidence intervals (CIs). All hypothesis tests yielding large p-value (e.g., $p > \alpha$) will be reported as being inconclusive. [name], the lead biostatistician, or her designee, will perform these analyses. Where necessary for parametric assumptions, appropriate transformations will be employed with justification for their use; otherwise, non-parametric tests will be used. P-values will be reported without dichotomization wherever applicable. Data obtained from transfusion events where units of the appropriate age could not be obtained (study deviation) will be excluded from a subanalysis of the dataset, and the same distribution of, and relationship between, variables will be explored with similar summaries, plots, and tree analysis as in the ITT analysis. All subjects, regardless of age and gender, will be analyzed together as one cohort. Statistical software used in this study will be Cytel, StatXact and LogXact, SAS version 9.4, and Salford systems CART (Classification and Regression Trees). To adjust for multiple comparisons, we will use the false discovery rate approach which is less conservative than the Bonferroni approach. *Missing data:* Logistic regression will be used to investigate the possible causes for missing data and to investigate if data are missing at random (MAR). Reasons for missing data will be documented in the study database. We do not anticipate any missing data or drop-outs, but we will monitor these events. Assuming data are MAR, multiple imputations will be used for items, and for repeated measures, a random effects models will be used; the structure for the variance covariance matrix will be explored under the constraints of sample size. A sensitivity analysis will also be performed to evaluate the robustness/fragility of the study's main results to reasonable perturbations of the statistical methods and assumptions used. Results of the sensitivity analyses will only be used to guide trust in the main results.

10.2.1 Primary Outcome Analysis

Key variables of interest:

PS – Measured as a percent of RBC positive

PE – Measured as a percent of RBC positive

Microparticles – Measured by number positive per microliter
CD62L – Measured as percent of monocytes positive
Plasma free hemoglobin – Measured as mg/dL
Non-transferrin bound iron – Measured as mg/dL
Rate of clinical infections – Measured as number per days on study

Aim 1:

The primary outcome measure is the proportion of biochemically old red cell units. Previous studies and our own work have suggested that PS, PE, and microparticles increase in a sigmoidal fashion over time.^{7,10} For this study, the cut-off for a biologically old unit would be the point at which the sigmoidal curve enters its log phase, which for PE, PS, and microparticles will be the mean value at day 21, or 8%, 3%, and 3/ μ L respectively based on these preliminary studies. This cutoff is biologically meaningful and is supported temporally by the metabolic changes that occur with red cell storage.¹¹⁹ Consequently, biochemically old units will be defined as having either a surface PE, surface PS, or a microparticle concentrations \geq the *a priori*-defined cutoff. We will compare the transfusions provided to the two groups (the proportion of biochemically old units when stored \geq 30 days compared to when stored \leq 10 days) using a Fisher exact test at an alpha of 0.05. Power: With a total sample size of 40 patients (20 in each group), we will have at least 80% power ($\alpha=0.05$) to detect a difference of at least 47% between the two randomized groups for biochemically old red cell units (close to a 100% difference is expected).

Exploratory: We will calculate the mean, minimum, and maximum levels of PS, PE, and microparticles for each study group, and we will compare the secondary outcome measures of plasma free hemoglobin, heme, and NTBI and also PS, PE, and microparticle concentrations using a two sided two sample t-test at an alpha of 0.05. We will also plan for auxiliary analyses that characterize the relationship between the PS level and the age (days) of the RBC units. This analysis will focus on estimation of the mean PS, PE, and microparticle level as a function of age (days), visualization of the data values, estimation of correlation coefficients, and evaluation of how well age (days) predicts PS, PE, and microparticle levels.

Aim 2:

The primary outcome measure is the change in CD62L (activated) circulating monocyte/macrophage MFI at 2 hours post-transfusion compared to the subject pre-transfusion. We will compare the two groups (\geq 30 day-old compared to \leq 10 day-old unit exposure) using a two sample two-sided t-test of the log at an alpha of 0.05. Power: We will have at least 80% power to detect a change in the ratio of 1.35 post-transfusion if the variability is similar to that seen in our preliminary data.

Exploratory: We will use a general(ized) linear model to include biochemically old units transfused (Aim 1 outcome), regardless of unit age, as a covariate in our analysis. Other co-variates in this model will include free heme, cell free hemoglobin, and NTBI. We will similarly compare other obtained activation measures as outcomes: activation markers for monocytes, neutrophils (as listed in section 6) and measured plasma cytokine

concentrations (section 6). We will also plan for auxiliary analyses of the outcome variables in which the explanatory variable is the age (days) of the RBC units --to characterize the degree to which age (days) can accurately predict the clinical and physiologic outcome measures defined. Lastly, as an exploratory aim, we will evaluate the *in vivo* change in recipient red cell PE/PS positivity at 2 and 24 hours post transfusion.

Aim 3:

The primary outcome variable is the rate of post-transfusion infections in the patient. The primary estimand is the treatment effect defined as the difference between the regimen-specific proportions of patients in the target populations that would experience post-transfusion infections. This population parameter will be estimated as a function of the proportions observed in the sample of patients studied. The point estimate will be reported along with the corresponding 95% confidence interval estimate. The presence of an indwelling catheter will be used as a key co-variate in this analysis. *Power:* A difference of 20% will be of clinical interest. We do not expect to have adequate power for this pilot study but at an alpha of 0.05 with 20 subjects in each group we will be able to detect a difference of 47% between the proportions.

Exploratory: We will explore the relationship of blood age and transfusion of biochemically old red cell units on the change in Hb and HbS% over time, daily pain scores (0-10 as an ordinal scale), opioid use and dose, ED and hospitalization rate, infection symptoms, new alloantibody formation, and antibiotic use during the 3-month study period. We will compare groups using a Fisher exact test. We will also plan for auxiliary analyses of the outcome variables in which the explanatory variable is the age (days) of the RBC units --to characterize the degree to which age (days) can accurately predict the clinical and physiologic outcome measures defined.

AIM 4:

We will calculate the mean, median, minimum, and maximum levels of each metabolic compound analyzed by [name] in his laboratory at the University of Colorado. Analysis tools and methods will be determined by his research team, and will focus on changes in the patient and the unit pre and post transfusion.

AIM 5:

Feasibility Analysis: We will assess important variables necessary to develop a future larger clinical trial on this subject. Areas that we will investigate during the course of this trial will include frequency and content of missing data, subject drop out rates, and estimates of outcome measure precision. For this study, we will evaluate the number of males, females, and adolescents that enroll in the study to inform future studies. We do not expect there to be differences in the key outcomes based on these variables, and plan to analyze all 40 subjects together as one cohort, but differences by age and gender will be evaluated and considered.

